10.1.1 Variables and derivations

End of trial classifications are defined as follows:

• Early withdrawal: Participants who exited the trial prior to completion for any reason other than being lost to follow-up, such as adverse event, protocol deviation/violation, death, withdrawal by investigator, withdrawal of consent or any other reason.

Note: Participants who withdraw from study or IP will continue to receive IPV until the course is complete. They will receive Rotarix® at standard scheduled time points according to the National Immunisation Program.

- Completed trial: Participants that completed all trial visits, as indicated in the 'End of Study' (CRF page 55).
- Lost to follow-up: Participants who exited the trial prior to completion due to being lost to follow-up (CRF page 55).

10.1.2 Analysis

If the study is prematurely discontinued, all available data will be listed, and a review will be carried out to determine which statistical analyses are considered appropriate.

Participant disposition and reason for withdrawal will be summarized and presented in data listings for the FAS population. The number of participants included in the relevant analysis populations, as well as the number of participants excluded with reasons for exclusion from the relevant analysis populations (Section 6) will be summarized and presented in data listings for the FAS population.

Protocol violations/deviations will be summarized for the SAF and ITT population and listed for FAS population.

11. Participant demographics and baseline characteristics

11.1.1 Variables and derivations

Trial completion, trial withdrawals, exclusions and protocol non-compliances will be summarized. Data for background and demographic variables will be listed by participant. Descriptive statistics will be provided. Medical history, current medical conditions, results of laboratory screening and baseline tests and any other relevant baseline information will be listed by participant. Previous and concomitant medication taken at any stage from birth and during the trial period will be listed by participant. Baseline for every participant will be defined as the last non-missing observation prior to the first exposure to IP.

The following demographic and baseline characteristics will be reported, to be collected from birth to 144 hours old (Day 1 of the study):

- Demographic data including date of birth, gender, ethnicity, gestational age and birth weight, age at IP administration date and height/length.
- Medical history (see section 14, page 39).
- All medications, supplements, traditional/complementary/herbal products and immunisations administered to the baby since birth (see section 14, page 39).
- All medications, supplements, traditional/complementary/herbal products and immunisations administered to the mother from 4 weeks pre-delivery (see section 14, page 39).
- Vital signs (see section 17, page 47).
- Physical examination (see section 18, page 48).

11.1.2 Analysis

Demographic data and baseline characteristics will be summarized for each treatment group for the FAS, SAF, ITT and PP populations and presented in data listings treatment group, participant number and visit for the FAS population. To see if certain participants are being excluded from PP analysis population, the Logistic regression will be performed on the demographic and baseline characteristics associated parameters as covariate with exclusion from the PP population and will be presented for the SAF population.

The Logistic regression model without categorical variable is as follows:

 $Y=\alpha + \beta (X)$

Where,

Y= The Per Protocol exclusion flag (Binary response).

 $\alpha = Intercept$

β =slope

X= Covariate i.e. Gender, Ethnicity, Gestational age (weeks), Birth weight (grams), Weight at Visit 1 (grams) and Age at IP administration (day)

The hypothesis is as follows

H0: β = 0

i.e. There is no statistically significant effect of respective demographics and baseline characteristics parameters on Per Protocol exclusion set

V/s

H1: β ≠ 0

i.e. There is statistically significant effect of respective demographics and baseline characteristics parameters on Per Protocol exclusion set.

The above hypothesis will be tested based on α (alpha)=0.05, if the p-value \geq 0.05 then we will conclude that there is no statistically significant effect of respective demographics and baseline characteristics parameters on Per Protocol exclusion set i.e. Ho is accepted.

Note: All continuous variables will fit into one model and all (binary and ordinary) variables will fit into other model separately.

12. Exposure to IP

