7.1.4 Statistical tests

A single analysis will be performed at the end of the trial. No interim analyses are planned.

Primary Analysis:

The primary analysis and primary sensitivity analysis are based on the per protocol population defined as participants who receive all 3 doses of RV3-BB and have no major protocol violations (after reviewed and agreed at the end of the study). Thirty percent of participants are expected to be excluded from the PP population due to death, study withdrawal, loss to follow-up, or study non-compliance.

Non-inferiority of the lower titre vaccine will also be assessed in the intention to treat population. The cumulative probability of response by 18 weeks of age will be estimated by the Kaplan-Meier method for each vaccine arm. The difference between high and low titre arms in the cumulative probabilities and its 95% confidence interval will be calculated. If the upper bound of the confidence interval is below 20%, non-inferiority of the lower titre vaccine will be demonstrated.

Additionally, we will calculate the 95% CI of the binomial proportions using the method of Newcombe-Wilson without continuity correction and generalized estimating equations (GEE) after dose 3 on the PP and ITT analyses set.

All the primary and primary sensitivity analysis will be based on PP and ITT analysis set.

See section 10 for additional details.

Secondary Analyses:

Immunogenicity and vaccine-take results will be (inferentially) analysed as done for the primary analysis. Descriptive analyses are described in section 10.

Safety

No formal statistical testing will be performed on the safety data.

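### The SAP's check on selective per-protocol exclusion accepts no effect whenever p ≥ 0.05 and tests two overlapping weights in one model, so it can give false reassurance about the primary analysis set

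*SAP*

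**What the plan says.** SAP 11.1.2 plans a logistic regression of a PP-exclusion flag on baseline characteristics, to see whether certain kinds of infant are being left out. The covariates are listed as "X= Covariate i.e. Gender, Ethnicity, Gestational age (weeks), Birth weight (grams), Weight at Visit 1 (grams) and Age at IP administration (day"). On model structure, the Note says "All continuous variables will fit into one model and all (binary and ordinary) variables will fit into other model separately". The result "will be presented for the SAF population". The rule is: "The above hypothesis will be tested based on α (alpha)=0.05"; at p ≥ 0.05 the conclusion is "no statistically significant effect of respective demographics and baseline characteristics parameters on Per Protocol exclusion set i.e. Ho is accepted".

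Treatment arm is not among the covariates. No joint test of the two weights and no confidence-interval criterion is given. SAP 7.1.4 says "Thirty percent of participants are expected to be excluded from the PP population", and SAP 6.1.4 makes PP the set for the primary analysis.

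**The concern.** Two features push the check towards reassurance.

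- **The acceptance rule.** A test that fails to reject may simply lack power. The SAP turns that outcome into a positive finding of no effect, with no margin or interval to show how large an effect remains compatible with the data.
- **The two weights.** Birth weight and a weight taken at most six days later measure nearly the same thing. In one model each coefficient is adjusted for the other, its standard error grows, and both can be non-significant although weight predicts exclusion strongly.

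A third feature limits what the model can say. Without treatment arm it gives no estimate of whether exclusion differs between arms, which is closer to what could distort the titre comparison.

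At stake is how readers interpret a primary set expected to omit about 206 of 688 infants (0.30 × 688 = 206.4).

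**Working it through.** **The plan's own figure.** The check has no stated power, but SAP 8.1.1 fixes its size. For 50% response in both arms, a margin of 0.20, one-sided 0.025 and 90% power:

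n = (1.960 + 1.282)² × (0.25 + 0.25) / 0.20² = 131.4, rounded up to 132 evaluable per arm.

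132 × 1.30 = 171.6, so 172 per arm and 688 in total. The plan's figure is reproduced. (Whether to multiply by 1.30 or divide by 0.70 is a separate matter.)

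**Inputs from the documents.** N = 688 at most (safety set), 30% excluded, two-sided α = 0.05, both weights in one model (SAP 7.1.4, 8.1.1, 11.1.2); Visit 1 within 144 hours of birth (SAP 7.1.1).

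**Assumptions, not in the documents.** Correlation r between the weights, 0.7 to 0.98. Gestational age correlates 0.5 with birth weight, and with Visit 1 weight only through birth weight. Age at dosing is independent. Exclusion depends on birth weight with log-odds slope of size 0.3 or 0.5 per SD (odds ratios 1.35 and 1.65).

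**Formula.** The chance that the birth-weight coefficient gives p ≥ 0.05 is about

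Φ(1.96 − β√(N p(1−p)(1−R²))),

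where R² comes from regressing birth weight on the other covariates. N p(1−p) = 688 × 0.30 × 0.70 = 144.48, with square root 12.02. Under the assumptions above, 1 − R² = 0.75(1 − r²)/(1 − 0.25r²).

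*Birth weight alone (R² = 0).* Slope 0.3: 12.02 × 0.3 = 3.61, and Φ(1.96 − 3.61) = 5%. Slope 0.5: Φ(1.96 − 6.01), about 0%.

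*Planned joint model:*

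| r | 1 − R² | Missed, slope 0.3 | Missed, slope 0.5 |
|---|---|---|---|
| 0.70 | 0.436 | 34% | 2% |
| 0.85 | 0.254 | 56% | 14% |
| 0.90 | 0.179 | 67% | 28% |
| 0.95 | 0.094 | 80% | 54% |
| 0.98 | 0.039 | 89% | 78% |

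For r = 0.90 and slope 0.3: 12.02 × √0.179 × 0.3 = 1.52, and Φ(1.96 − 1.52) = 67%.

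Simulating the four-covariate logistic model under these assumptions agrees to within a few points: about 35–88% missed at slope 0.3 and about 2–79% at slope 0.5.

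**Which test is missed.** The table concerns the birth-weight coefficient. The chance that all four continuous covariates are accepted is somewhat lower: for r from 0.85 to 0.98, about 49–78% at slope 0.3 and 13–69% at slope 0.5. In a second simulation (odds ratio 1.3 per SD, r = 0.9, gestational-age correlation 0.4), neither weight was significant in 70% of runs. A joint 2-df test of both weights missed in 27%, and birth weight alone in 12%.

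**The acceptance rule without collinearity.** For an uncorrelated covariate with odds ratio 1.2 per SD, ln 1.2 = 0.182, 12.02 × 0.182 = 2.19, and Φ(1.96 − 2.19) = 41%. The rule would accept no effect in about two trials in five.

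**Treatment arm.** If arm were added, true exclusion of 30% against 40% in two arms of 172 would reach p < 0.05 with power Φ[(0.10√172 − 1.96√(2 × 0.35 × 0.65)) / √(0.30 × 0.70 + 0.40 × 0.60)] = Φ(−0.02) = 49%. Another accept-or-reject rule would be no better; an estimate with an interval is needed.

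**The case against.** The strongest reply is that nothing hangs on this check. No rule in the SAP uses its result, PP is primary either way, and non-inferiority is also assessed in the ITT set. That stands, and it keeps the point minor. The ITT set is a partial safeguard only: SAP 6.1.3 requires a dose and evaluable baseline and post-baseline blood samples, and labels its analyses supportive.

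A reader might infer that exclusion differing between arms could not be detected at all. The documents do not support that. SAP 10.1.2 summarises exclusions with reasons, SAP 20.1.13 makes summary tables by treatment group the default, and SAP 11.1.2 tabulates baseline characteristics by group in the FAS, SAF, ITT and PP sets. Exclusions are also decided at a blinded review meeting (SAP 6). The gap is that the model does not estimate the difference.

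A reader might also infer that real selection of any kind would usually be declared absent. That goes too far. For a covariate without a near-duplicate, an odds ratio of 1.3 or more per SD is missed about 12% of the time or less, and a 10-point difference by gender is detected with 82% power. The large miss rates are specific to weight.

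The correlation and slopes are assumptions. Eligibility limits on weight (Protocol 5.2.3) tend to lower the correlation, and at r = 0.7 with slope 0.5 the miss rate is only about 2%. Nothing in the documents says that weight drives exclusion. Finally, the printed equation has a single covariate, which could suggest separate fits; the Note says otherwise, and I follow the Note.

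**Conclusion.** Wrong as written, minor severity. The inference from p ≥ 0.05 to no effect is invalid whatever the correlation, and putting both weights in one model makes it worse for weight-related selection.

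The size depends on the assumed slope and on a correlation the documents do not give. At slope 0.3 the joint model does clearly worse than one weight over the whole range from 0.7 to 0.98. At slope 0.5 the loss is trivial at 0.7 and large from about 0.9 upwards.

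The primary estimate and its decision rule are unaffected. It would be tempting to say that the check will be used to defend a biased PP result, but no section gives it that role. The harm is a misleading statement in the report that PP exclusion is unrelated to infant characteristics.

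**What to change.** In SAP 11.1.2:

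1. Enter only one of the two weights in the continuous-covariate model, or fit each covariate separately, and make the printed equation and the Note agree.
2. Delete the sentence that accepts the null hypothesis, and draw no conclusion of no effect from p ≥ 0.05.
3. Report odds ratios with 95% confidence intervals, so that readers see how much selection the data leave open.
4. Add treatment arm as a main effect, reported as an estimate with its interval.

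Arm-by-covariate terms are optional. They have little power: in simulation, selection on birth weight confined to one arm was detected by the 3-df interaction test with 24% power at slope 0.3 and 56% at slope 0.5.

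The cost is a change of SAP wording, minor reprogramming and a few more table rows. No new data are needed. Dropping one weight from the joint model gives up a mutually adjusted estimate that would be imprecise anyway if the weights are highly correlated; separate fits keep both weights in the report.

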12.1.1 Variables and derivations

In eCRF IP Administration form we are capturing the treatment dosing related data and the dates of first IP administration will be derived as the first date of dosing from the IP Administration form in eCRF. The date of last IP administration will be derived as the date of last dose of IP from the End of the Study form in eCRF page.

12.1.2 Analysis

Based on the completion of the IP Administration pages in the CRFs, IP administration data will be summarised and presented in data for the FAS and ITT population.

13. Treatment Compliance

13.1.1 Variables and derivations

Treatment compliance will be derived as a dichotomous variable. A participant will be considered compliant with study treatment if they received the scheduled administration of all doses of the IP, within the protocol specified time windows. Any incomplete administration of IP will be recorded in the participant notes and the CRF.

Administration of any dose of IP can be delayed at the discretion of the investigator or Medical Monitor however, if the second, third or fourth doses fall outside of the protocol specified window it will be recorded as a protocol deviation.

Additional protocol specified time windows were included to assist in keeping participants compliant with local authority regulations for the receipt of vaccines in the National immunisation program.

Assessment windows for treatment compliance relating to IP administration are

- Visit 1 (Day 1; <=144 hours of age)
- Visit 3 (Week 6; +7 days),
- Visit 5 (Week 10; ±7 days),
- Visit 7 (Week 14; ±7 days),

13.1.2 Analysis

Based on the completion of the IP Administration pages in the CRFs, compliance for each participant at each administration visit will be reported. IP administration data as well as compliance data will be summarised and presented in data listings for the FAS and ITT population.

14. Medical and treatment history

14.1.1 Variables and derivations

Medical history will be coded using the MedDRA central coding dictionary, Version (refer Data Management Plan (DMP) for version number).

14.1.2 Analysis

Medical history will not be analysed but will be presented as data listings for the FAS.

15. **Previous and concomitant medications**

15.1.1 Variables and derivations

Infant and maternal concomitant medications will be documented in the participant's CRF. This will include all prescription and non-prescription medication, traditional, herbal and complementary medicines given to the participant from birth until end of study will be recorded.

In addition, prescription and non-prescription medication including traditional, herbal and complementary medicines taken by the mother will be recorded from 4 weeks prior to delivery, during delivery, and post-delivery until end of study (or until cessation of breastfeeding).

Concomitant medication records will include the drug name, total daily dose, route of administration, start and stop date of administration, and indication (for participants only).

Indication List: Anaemia, Anaemia in pregnancy, Anaemia prevention in pregnancy, Anaemia prophylaxis, Anaesthesia, Antenatal, Anthelmintic, Anti biotic, Anti malaria drug, Anti retro viral therapy, Antibiotic, Anti-emetic, Antiemetic post ceaserian section, Antiretroviral therapy, ART, ARVS, Asthma, C/S pain, Contrimoxazole preventive therapy, Cough, CPT, Diarrhoeam, Elevated blood pressure, For rehydration, HAART, HIV related neuropathy, Indication anaemia, Infection prevention after returned placent removal, Infection prevention post ceaserian section, Infection prevention post evacuation, IPT Iron supplement, Isonazide preventive therapy, Isoniazid prophylaxis therapy, Lower abdominal pain treatment, Malaria, Malaria prophylaxis, Malaria prophylaxis in pregnancy, Mastitis, Minimise bleeding post delivery, MOH antenatal protocol, Neuropathy prophylaxis, Oesophageal reflux, Pain, PCP prophylaxis, Peripheral neuropathy, Pneropathy prophlaxis and treatment, Pneumocystis carinii pneumonia (CPC) prophylaxis, Pneumonia cariri prophylaxis, Pneumonia prophylaxis, PNP, Post caeser, Post delivery arrest of haemorrage, Post delivery pain, Post op prophylaxis, Post op surgery, Post partum pain killer, Post sugical-mastitis, Postpartum hahituage (p.p.h.20 cervical tear), Pre and post surgery antibiotics, Precaution of anaemia in pregnancy, Prevention of anaemia, Prevention of anaemia during pregnancy,

Prevention of anaemia in pre and post delivery, Prevention of infection, Prevention of opportunistic infections, Prevention of peripheral neuropathy, Promote uterine contraction (prevents bleeding), Prophylaxis after ceaserian section, Prophylaxis after ceaserian section (pain), Prophylaxis after ceaserian section(antibiotic), Prophylaxis and treatment for neuropathy, Prophylaxis for neuropathy, Prophylaxis for PCP antibiotic, Prophylaxis for tuberculosis antibiotic, Prophylaxis of anaemia in pregnancy, Prophylaxis pinaemia, Prophylaxis therapy for co-infection, Puerperial sepsis, Rash, Sepsis, Sexually transmitted infection treatment, Supplementation, Syphilis treatment, TB prophylaxis, to prevent anemia in pregnancy, Treatment of HIV and AIDS, Treatment of infection, Tuberculosis prophylaxis, Upper respiratory tract infection, Urinary tract infection treatment, UTRI, Vitamin supplement.

'Previous medications' are defined as any medication received as well as stopped prior to first administration of the IP.

Previous/concomitant medications' are defined as any medication received prior to first administration of the IP however, only stopped after first administration of the IP, during the trial until Visit 9.

Concomitant medications' are defined as any medication where the start date is after first administration of the IP, during the trial until Visit 9.

Where necessary, start and end dates for concomitant medications will be imputed as follows:

The imputations derived for partial dates will be as follows:

- Imputation on the concomitant medication receive date:
 - if only the day-part is missing, and the month and year are equal to treatment start month and treatment start year OR if both the day- and month-part are missing, and the year is equal to treatment start year, then the minimum of treatment start date and concomitant medication end date is used;
 - in all other cases the missing day-part becomes the 1st day of the month, and the missing month-part becomes the 1st month of the year.

- Imputation on the concomitant medication end date:
 - if only the day part is missing then the last day of the month is used if this does not result in a date after the subject's trial exit date (e.g. death) in which case the trial exit date will be used;
 - if the day and month part are missing then the last day of the month and Last month of the year (i.e. 31DEC) are used if this does not result in a date after the subject's trial exit date (e.g. death) in which case the trial exit date will be used;
 - in all other cases the concomitant medication end date will not be imputed.

All medications will be coded using WHO-DD (refer Data Management Plan (DMP) for version number).

15.1.2 Analysis

Previous- and concomitant medications will be presented in data listings for the FAS populations. All medications captured in the eCRF will be categorised as either '*Previous medications*', '*Previous/concomitant medications*' or '*Concomitant medications*' and separate listings for infant and maternal. Listing will be presented by Standardized Medication Name and Reported Term.

16. Adverse events

All safety parameters (adverse events (AEs), and the occurrence of blood in the stool) will be summarized descriptively by treatment group. The descriptive statistics will include the number of observations, mean, standard deviation, median, minimum and maximum for continuous variables and number of observations and their percentages and number of participants for categorical variables.

AEs will be coded using MedDRA version (refer Data Management Plan (DMP) for version number) and will be presented by system organ class and preferred term for each treatment group. Coding details are available in the Data Management Plan.

16.1.1 Variables and derivations

Adverse Events (AEs) will be defined as events that started at the time of, or after the, first IP administration, as well as those events that started prior to the first study drug administration, but which worsened after the first study drug administration.

Imputations will only be performed where at least the year is provided. The imputations derived for partial dates will be as follows:

- Imputation on the AE start date:
 - if only the day-part is missing, and the month and year are equal to treatment start month and treatment start year OR if both the day-part and month-part are missing, and the year is equal to treatment start year, then the minimum of treatment start date and AE end date is used;
 - o therwise the missing day-part becomes the 1st day of the month, and the missing month-part becomes the 1st month of the year.
- Imputation on the AE end date:
 - if only the day part is missing then the last day of the month is used if this does not result in a date after the subject's trial exit date (e.g. death) in which case the trial exit date will be used;
 - if the day and month part are missing then the last day of the month and Last month of the year (i.e. 31DEC) are used if this does not result in a

date after the subject's trial exit date (e.g. death) in which case the trial exit date will be used;

- \circ in all other cases the AE end date will not be imputed.
- There will be no default for a missing year field.

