10.5 Doses and treatment regimens

Approximately 688 participants will be prospectively randomised to one of the following four treatment groups in a 1:1:1:1 ratio.

- High dose neonatal RV3-BB vaccine schedule (1x10⁷titre dose). RV3-BB Vaccine for doses 1, 2 and 3 and placebo for dose 4
- Mid dose neonatal RV3-BB vaccine schedule (3x10⁶titre dose). RV3-BB Vaccine for doses 1, 2 and 3 and placebo for dose 4.
- Low dose neonatal RV3-BB vaccine schedule (1x10⁶titre dose). RV3-BB Vaccine for doses 1, 2 and 3 and placebo for dose 4.
- High dose Infant RV3-BB vaccine schedule (1x10⁷titre dose). Placebo for dose 1 and RV3-BB Vaccine for doses 2, 3 and 4

Participants will also receive a dose of commercially available Rotarix® at 18 weeks of age.

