7.1.1 Visit and date conventions

Visit day will be calculated from the reference treatment start date which will be used to present start/stop day of assessments and events. The reference treatment start date is defined as the date of first IP administration. The following conventions will be used for visit references:

- Visit day = date of event reference treatment start date
- Visit week = $\frac{visit \, day}{7}$, rounding up to next whole number

No visit windowing (i.e. remapping of visits based on visit windows) will be performed for this trial. The assigned nominal visit will be used for by-visit summaries. In the situation where the assessment/event date is partial or missing, visit day/week/month, and any corresponding durations will appear missing in the data listings. Unscheduled measurements will not be included in by-visit summaries. Trial visit will be assigned as below (see section 4.3, Schedule of Events):

Pre-study: Second trimester to birth

Preliminary consent, cord blood collection and maternal blood sampling will happen during this period.

Visit 1 (Day 1; birth to 144 hours old)

Participants will return to the trial site for Day 1 procedures and maternal blood samples will be collected.

Visit 2 (Day 8; 7±1 days post visit 1), Visit 4 (Week 7; 7±1 days post visit 3), Visit 6 (Week 11; 7±1 days post visit 5), Visit 8 (Week 15; 7±1 days post visit 7)

Participants will return to the trial site for vital sign measurements, feeding review, AE and concomitant medication recording.

Visit 3 (Week 6; + 7 days), Visit 5 (Week 10; \pm 7 days and at least 21 days post visit 3), Visit 7 (Week 14; \pm 7 days and at least 21 days post visit 5), Visit 9 (Week 18; \pm 7 days and at least 21 days post visit 7)

Participants will return to the trial site for Week 6/10/14/18 procedures.

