16.1.2 Analysis

All summaries and listings for safety parameters (adverse events (AEs) will be based on the SAF population.

In order to be able to compare the neonatal vaccine schedule to the infant vaccine schedule after 3 doses of RV3-BB, due to the different time points of vaccination between the two different schedules, summaries of AEs are presented based on doses 1-3 of investigational product for the neonatal schedule and doses 2-4 of investigational product for the infant schedule. Hence, only AEs that started after the time of administration of the investigational product up to 28 days following each dose will be summarised for doses 1, 2 and 3 for the neonatal comparison and for doses 2, 3 and 4 for the infant comparison. In addition, some summaries will be presented by dose with an overall summary of AE (as presented for the DSMB).

Summaries (and listings where applicable) will be presented for all participants. For summaries, all safety data will be presented by dose number unless otherwise specified.

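### SAP 16.1.1 anchors day-missing AE start dates only to the first IP dose, so about half of those after doses 2-4 fall before the dose they followed; the main loss is after the infant arm's first RV3-BB dose

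*SAP*

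**What the plan says.** SAP 16.1.1 (Adverse events) has two branches for a missing start day. The first applies where "the month and year are equal to treatment start month and treatment start year"; "then the minimum of treatment start date and AE end date is used". It also covers a date with day and month both missing, if the year is the treatment start year. In all remaining cases "the missing day-part becomes the 1st day of the month, and the missing month-part becomes the 1st month of the year".

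SAP 7.1.1 fixes the anchor: "The reference treatment start date is defined as the date of first IP administration". Protocol 10.5 gives the infant arm "Placebo for dose 1 and RV3-BB Vaccine for doses 2, 3 and 4", so its anchor is a placebo dose. In the neonatal arms doses 1-3 are RV3-BB and dose 4 is placebo.

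SAP 16.1.2 bases the AE summaries on "doses 1-3 of investigational product for the neonatal schedule and doses 2-4 of investigational product for the infant schedule". Within those doses, "only AEs that started after the time of administration of the investigational product up to 28 days following each dose will be summarised". It adds that "all safety data will be presented by dose number unless otherwise specified".

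**The concern.** A single-anchor rule suits a trial that only needs to know whether an AE began on treatment. Here the tables need to know which of four doses an AE followed, and whether it began within 28 days of that dose. No branch of the rule refers to doses 2, 3 or 4.

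The anchor protects the first RV3-BB dose in the neonatal arms but only the placebo dose in the infant arm. At stake are the by-dose AE tables and the descriptive safety comparison of the two schedules. An infant-arm AE that followed the first RV3-BB dose can be dated to the placebo period, or to a gap between windows, and then drops out of the dose 2-4 summary.

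**Working it through.** The plan states no figure for this, so there is none to reproduce.

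**Inputs from the documents.** Dose 1 is given by 144 hours (6 days) of age (Protocol 5.2.3). Dose 2 is given no earlier than 6 weeks (42 days), with a +7 day window (Protocol 6.5). Doses 3 and 4 are due at weeks 10 and 14, ±7 days, at least 21 days after the previous dose (Protocol 6.7, 6.9). Recruitment lasts about 9 months (SAP 4.1.2).

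**Assumptions.** Onset is uniform over days 0-28 after a dose and before the next dose; days 0-7 is the alternative. Doses fall either at exact weeks or spread over the visit windows.

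**Step 1: does the anchor ever cover doses 2-4?** The smallest gap from dose 1 to dose 2 is 42 − 6 = 36 days, longer than any month. A day-missing AE after dose 2, 3 or 4 can never share a month with dose 1, so the first branch covers 0% of them.

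**Step 2: how often is the AE placed before its own dose?** This happens when AE and dose share a calendar month and the dose was not on the 1st. A direct count for dose 4, which has no later IP dose, uses 29 possible onset days:

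- 30-day month: 435 of 30 × 29 = 870 combinations, 50%.
- 31-day month: 464 of 31 × 29 = 899 combinations, 52%.
- Onset on days 0-7, 30-day month: 204 of 30 × 8 = 240 combinations, 85%.

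**Step 3: where do the AEs go?** Results from simulated dose calendars (300,000 infants); the range runs over the two dose-timing assumptions:

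| Dose followed | Placed before own dose | Infant arm: leaves the dose 2-4 summary | Neonatal arms |
|---|---|---|---|
| 2 | 52-57% | 52-57% (17-22% to the placebo window, 30-40% to no window) | 17-22% to dose 1, 30-40% to no window |
| 3 | 52-55% | 0.2-4% | 0.2-4% to no window; the other moves go to dose 2 |
| 4 | 51% | 0-5% | 45-51% to the dose 3 window |

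With onset on days 0-7, about 85% are placed before their own dose, for each of doses 2-4.

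**Step 4: examples.** Dose 1 (placebo) is on 14 February and dose 2 on 28 March. An AE on 30 March with the day missing becomes 1 March, 15 days after placebo and 27 days before dose 2. An AE on 3 April becomes 1 April, still 4 days after dose 2.

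**Step 5: net effect, assuming equal numbers of day-missing AEs after each dose.**

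- Infant summary: loses (0.522 + 0.002 + 0)/3 = 17% to (0.568 + 0.036 + 0.050)/3 = 22%.
- Neonatal summary: loses 0.299 + 0.002 = 0.301 to 0.395 + 0.036 = 0.431 of one dose's day-missing AEs. It gains 0.505 + 0.002 = 0.507 to 0.446 + 0.011 = 0.457 from dose 4. The net change is +0.206/3 = +7% to +0.026/3 = +1%.
- Overall size: if 1% to 5% of AEs have a missing start day (assumed), the infant summary loses about 0.17 × 1% = 0.2% to 0.22 × 5% = 1.1% of its AEs.

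**Day and month both missing.** If the year is the treatment start year, the AE goes to the dose 1 date, or to the AE end date if earlier. In the infant arm dose 1 is placebo.

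**The case against.** The strongest reply is that the rule may rarely operate. Protocol 11.3 requires start and stop dates. Staff contact families the day after each dose, again on day 3, 4 or 5, at a visit about a week later, and at least weekly throughout. Diarrhoea has a dated log (Protocol 8.4), and monitors review CRFs for completeness (Protocol 14). Partial dates are least likely in the first week, where the 85% figure applies. This stands: the 1-5% range is an assumption and may be too high.

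Dose number might also be read from a CRF field instead of being derived from dates. The SAP does not say so, and the 28-day window would still depend on the start date.

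Four stronger readings are tempting, and the documents do not support them:

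- **All AEs after doses 2-4 move.** Only day-missing AEs sharing a month with a dose not given on the 1st do, plus the case with both day and month missing. In the infant arm, 95-100% of day-missing AEs after doses 3 and 4 stay in the dose 2-4 summary; where they move, only the dose credited changes.
- **The rule is shown to favour the infant schedule.** Step 5 leans that way, but it assumes equal AEs per dose. The neonatal arms also lose dose 2 AEs, which partly offsets the dose 4 AEs they gain. The documents give neither AE rates by dose nor the frequency of partial dates.
- **AEs vanish from the report.** SAP 16.1.2 and 16.1.3 also provide overall summaries.
- **The SAP breaks its own worst-case principle.** Those rules (SAP 16.1.3, 16.1.5) cover seriousness and relatedness, not dates. SAP 15.1.1 uses much the same date convention for concomitant medication.

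**Conclusion.** The concern holds and is small. The date rule does not fit the by-dose windows, and nothing else in the protocol or SAP corrects it. About 51-57% of day-missing AEs after doses 2-4 are placed before the dose they followed. The consequence that matters is the loss of 52-57% of day-missing infant-arm AEs after the first RV3-BB dose. In the neonatal arms 30-40% of day-missing dose 2 AEs fall in no window, and placebo AEs after dose 4 can appear under dose 3.

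These shares rest on the assumed onset pattern. The absolute effect depends on a partial-date rate that the documents do not give and that is probably low. SAP 7.1.4 plans no formal safety testing, so no inference is affected. It is worth correcting because the change is cheap.

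**What to change.** Replace the second branch in SAP 16.1.1, before database lock, with this order:

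1. If the CRF or contact records show which dose the AE followed, impute to that dose date.
2. Otherwise, if the known month (or year) contains IP doses, impute to the latest RV3-BB dose date in that period that is not after the recorded AE end date.
3. Use a placebo dose date only if no RV3-BB dose qualifies.
4. Use the 1st of the month only if no dose qualifies.

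State that a start imputed to a dose date counts as after that dose, and flag imputed starts in the by-dose tables.

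**Gain.** A simpler rule (latest IP dose of either kind, not after the end date) was tested with assumed AE durations of 0-5 days. With the end date known, correct placement for doses 2-4 rose from 43-50% to 91-100%.

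**Cost.** A few SAP sentences and a small programming change. Steps 2 and 3 need the allocated dose sequence, so the code should be fixed beforehand and run after unblinding. If the end date is also missing, some AEs will be charged to a later dose than the one they followed. Under the simpler rule this moved about half of day-missing neonatal dose 3 AEs to the dose 4 placebo, and about 14% of infant placebo-dose AEs to RV3-BB dose 2. Preferring RV3-BB doses reduces the first of these, but such AEs still move when dose 4 is the only dose in that month. Step 1 is therefore the most useful part.
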